#### **Section 6.1 (Data Collection and Submission)**

- CTSU Template language has been updated.
- In section 6.1.1, the following information has been added to the list of baseline reports: ‘Germline mutation testing report when requested by Alliance Statistics and Data Management Center to resolve discordant data entries.’

#### **Section 11.1 (Schedule of Evaluations)**

- A third sentence has been added to the second bullet point: ‘After the end of FOLFOX treatment, the timing of CEA should correspond with the timing of radiographic imaging, where possible, but more frequent testing is at provider discretion.’

#### **Section 12.0 (End of Treatment)**

- [Sections 12.4](#) (Survival Follow-Up) and [12.5](#) (Lost to Follow-up) have been added.

[Appendix V](#) (AIO Sites and Investigators) has been added back into the protocol. It was removed by mistake in a previous update. The remaining appendices have been renumbered.

‘Gender’ has been replaced with ‘Sex’ throughout the protocol document ([schema](#), [eligibility](#) and [Correlative Science Companion Studies](#) sections) as directed by NCI.

---

#### **UPDATES TO THE MODEL CONSENT:**

No changes to the model consent form.

**A replacement protocol and consent document have been issued.**

---

**RANDOMIZED TRIAL OF STANDARD CHEMOTHERAPY ALONE OR COMBINED WITH ATEZOLIZUMAB  
AS ADJUVANT THERAPY OF PATIENTS WITH STAGE III COLON CANCER  
WITH DEFICIENT DNA MISMATCH REPAIR**

**Eligibility Criteria (see Section 3.0)**

Histologically proven stage III colon adenocarcinoma  
 Presence of deficient MMR (dMMR) via IHC  
 Completely resected tumors  
 Entire tumor in colon  
 No evidence of residual involved lymph node disease or metastatic disease  
 Patients known to have Lynch Syndrome are eligible  
 No other planned concurrent investigational agents or other tumor directed therapy  
 No active autoimmune disease, including colitis, panhypopituitarism, adrenal insufficiency  
 No known active hepatitis B or C infection  
 No active pulmonary disease with hypoxia  
 No grade  $\geq 2$  peripheral motor or sensory neuropathy  
 Non-pregnant, non-nursing  
 Age  $\geq 12$  years  
 Performance Status: Lansky  $\geq 50\%$  (patients  $<16$  years), Karnofsky  $\geq 50\%$  (patients 16 to  $<18$  years), or ECOG PS  $\leq 2$  (patients  $\geq 18$  years)

[figure not shown]
**Required Initial Laboratory Values**

Absolute Neutrophil Count (ANC)	$\geq 1500/\text{mm}^3$
Platelet Count	$\geq 100,000/\text{mm}^3$ *
AST/ALT	$\leq 2.5 \times \text{ULN}$
Bilirubin	$\leq 1.5 \times \text{ULN}$ ***
TSH	WNL****
Creatinine	$\leq 1.5 \times \text{ULN}$

**OR**Calculated Creatinine Clearance  $\geq 45 \text{ mL/min}$ \*\*\* Platelets  $\geq 75,000$  for patients who received Cycle 1 of mFOLFOX6 prior to registration\*\* By Cockcroft-Gault equation. Alternatively, for patients  $<18$  years of age, maximum serum creatinine  $\leq$  the age-sex-specific norms listed in Section 3.2.7

\*\*\* Except in the case of Gilbert disease

\*\*\*\* Supplementation is acceptable to achieve a TSH WNL

**Schema**

\* 1 cycle = 14 days. One cycle of mFOLFOX6 is allowed prior to registration. If Cycle 1 of mFOLFOX6 is started prior to registration, then the first post-registration cycle will be mFOLFOX6 Cycle 2. For patients who received Cycle 1 of mFOLFOX6 prior to registration and who are randomized to Arm 1, atezolizumab will start with Cycle 2 of mFOLFOX6.

\*\* Assessment of dMMR status for eligibility may be performed locally or at a site-selected reference laboratory. Retrospective central confirmation of dMMR testing is required for all patients to gauge the false-positive rate in local testing (not for eligibility). See Section 6.2 for specimen submission requirements.

\*\*\* The standard of care for the time window between the end of mFOLFOX6 Cycle 1 and the start of mFOLFOX6 Cycle 2 is 14 days; however, up to 28 days are allowed between the end of Cycle 1 and the start of Cycle 2 if delays are made due to toxicity.

**Patients will be followed for recurrence and survival every 6 months for the first two years after registration, then survival every 6 months and recurrence once annually for years 3-5 after registration, and then survival every 6 months for years 5-8 after registration.**

## 1.0 BACKGROUND

### 1.1 Colorectal Cancer

In the United States, colorectal cancer (CRC) is the fourth most common malignancy and the second most frequent cause of cancer-related death [1]. Surgery is the primary modality of treatment for non-metastatic CRC, and a resection with ‘curative intent’ occurs in 80-85% of patients with stages I-III disease. Among patients with potentially curable CRC, pathologic stage (including depth of invasion into the bowel wall, involvement of regional lymph nodes, and distant metastasis) is critical in determining prognosis and whether chemotherapy treatment in addition to surgery is necessary. Overall, 35-40% of CRC patients have stage III disease at diagnosis (~50,000 people in the United States annually) [2]. Among patients with stage III colon cancer, ~30-50% will develop cancer recurrence (dependent on substage of stage III disease and other factors) despite curative-intent surgery and postoperative adjuvant chemotherapy.

#### Pediatric Colorectal Cancer

Colorectal cancer (CRC) is rare in the pediatric population, with approximately 350 patients ages 19 and under in the U.S. per year. Compared to adults, pediatric patients with CRC are more likely to have tumors with unfavorable histology and stage 3 and 4 disease [3]. Prognosis for these patients remains poor, with 5-year overall survival of approximately 40% [4]. Despite this, no pediatric specific CRC studies have been performed to date. Instead, the majority of pediatric patients are treated using adult protocols despite lack of data on pediatric outcomes [3]. CRC in the pediatric age group is often hereditary of which the most common hereditary susceptibility is due to Lynch Syndrome [5]. In patients with Lynch Syndrome, CRC usually presents after the 4th decade of life; fewer cases have been reported in children and adolescents. Pediatric and adult colon cancers from patients with Lynch Syndrome show deficient DNA mismatch repair and are thus, potential candidates for participation in A021502.

### 1.2 Adjuvant Chemotherapy

The current standard of care for the adjuvant therapy of stage III colon cancer is oxaliplatin coupled with 5-fluorouracil infusion (FOLFOX-6) for 12 cycles (every 2 weeks) or 6 months. In 2003, the first analysis of the Multicenter International Study of Oxaliplatin/Fluorouracil/Leucovorin in the Adjuvant Treatment of Colon Cancer (MOSAIC) study was presented and showed a statistically significant improvement in disease-free survival with the addition of oxaliplatin to 5-fluorouracil plus leucovorin in stage III patients.[6] An update of the MOSAIC trial demonstrated a 5-year disease-free survival of 66% with FOLFOX compared to 59% with 5-fluorouracil and leucovorin that was limited to stage III patients.[7] The addition of oxaliplatin to fluoropyrimidine therapy increases the risk of toxicities, including bone marrow suppression and neurosensory symptoms, of which the latter is particularly problematic for some patients. At the completion of therapy in the MOSAIC trial, 12% of patients had grade 3 peripheral neuropathy and 92% had some level of neuropathy [8]. In a recent update, 15% of patients still had some level of residual neuropathy 4 years after the completion of adjuvant therapy.[7] Progress in the adjuvant therapy of colon cancer has stalled overall based upon the failure of targeted agents including anti-VEGF (bevacizumab) or anti-EGFR (cetuximab or panitumumab) antibodies to improve outcomes in patients with stage III disease in contrast to evidence of benefit in the metastatic setting [9-11].

Clinical trials being conducted in the U.S. and Europe are testing the hypothesis that 3 months of adjuvant FOLFOX orXELOX is non-inferior to 6 months. The IDEA (International Duration Evaluation of Adjuvant Chemotherapy) steering committee was formed to prospectively pool data from multiple ongoing trials. The TOSCA trial in Italy is randomizing 3450 high-risk stage II and stage III patients to 3 versus 6 months of adjuvant FOLFOX with an option for additional randomization to bevacizumab in stage IIIC patients. The SCOT trial in the UK is randomizing approximately 6500 stage II and III colon and rectal cancer patients to 3 versus 6 months of adjuvant FOLFOX/XELOX. In addition, the GERCOR and C80702 trials are each enrolling 2000-2500 patients with stage III colon cancer to an adjuvant trial of 3 versus 6 months of FOLFOX, and smaller trials are also being conducted in Japan and Greece. Results of the IDEA pooled analysis of over 12,000 patients has been published and did not meet the non-inferiority cutoff. A non pre-specified risk analysis stratified patients into low and high risk based on T and N stage. Among patients with low risk tumors (T1-3N1), 3 months of therapy was non inferior to 6 months. However, 3 months of the FOLFOX regimen was inferior to 6 months in patients with high-risk tumors (T4 and/or N2) [12]. Importantly, the study did not analyze tumors for dMMR status, so no data is yet available for this tumor subset. Accordingly, the duration of FOLFOX will remain 6 months in the ATOMIC trial as risk stratification in IDEA is unknown for patients with dMMR tumors.

### 1.3 DNA Mismatch Repair Deficient Colon Cancers

Two primary pathways of CRC have been described and include tumors with chromosomal instability (CIN) or those with microsatellite instability (MSI). MSI colon cancers are typically right-sided, poorly differentiated and contain abundant tumor infiltrating lymphocytes (TILs). MSI is a consequence of deficient DNA mismatch repair (dMMR) that is sporadic in origin in two-thirds of cases and is hereditary in one-third due to Lynch Syndrome (LS). LS is caused by a germline mutation in one of four MMR genes (MLH1, MSH2, MSH6, PMS1) with those in *MLH1* or *MSH2* accounting for more than 90% of cases [13]. Epigenetic inactivation of *MLH1* occurs in sporadic MSI CRCs and such tumors are enriched in *BRAF*V600E mutations [14]. CRCs with MSI/dMMR have been generally reported to have a better prognosis compared to tumors with proficient (p) MMR that are microsatellite stable (MSS). Data indicate that the association of dMMR/MSI with favorable prognosis is stronger in stage II versus stage III patients [15]. In this regard, dMMR status was not significantly associated with better overall survival in stage III colon cancers treated with the standard FOLFOX regimen in pooled data from 3 recent adjuvant chemotherapy trials (NCCTG N0147, PETACC-8, NSABP C-08) (unpublished data). Of note, the frequency of N2 disease (4 or more metastatic regional lymph nodes) which is a poor prognostic factor was similar among dMMR compared to pMMR colon cancers in the NCCTG N0147 trial [16]. Accordingly, there is an unmet need to improve outcomes in patients with stage III dMMR/MSI colon cancers.

### 1.4 MSI and Immune Checkpoint Inhibition

MSI/dMMR CRCs are hypermutated and express abundant neopeptides that elicit a robust T cell immune response characterized by abundant tumor infiltrating lymphocytes (TILs) [17]. These TILs include cytotoxic CD8+ T cells as well as activated Th1 cells, characterized by IFN $\gamma$  production and the Th1 transcription factor, TBET [17]. However, recent data indicate that this robust immune reaction fails to eradicate the tumors due to immune checkpoint proteins that are overexpressed in MSI/dMMR tumors compared to p(MSS cancers [17]. These findings link tumor genotype with the immune microenvironment, and may explain why MSI/dMMR tumors are not eliminated despite the anti-tumor Th1/CTL microenvironment. They further suggest that

blockade of specific checkpoints may be selectively efficacious in the MSI/dMMR subset of CRC. In this regard, checkpoint inhibitors can enable a patient's own T cells to eradicate tumor cells which appears to underlie the observed efficacy of an anti-programmed death-1 (PD-1) antibody in cancers with MSI-H. Specifically, a recent phase II study in patients with MSI-H metastatic CRCs and MSI-H non CRCs (from Lynch Syndrome patients) showed that antiPD-1 antibody, pembrolizumab, as monotherapy produced a 57% response rate in MSI-H tumors compared to 0% in MSS tumors, and PFS has not yet been reached [18]. This modest size patient cohort included CRC patients with Lynch Syndrome (LS), some sporadic MSI-H tumors, and extracolonic malignancies associated with LS. While only 4% of metastatic CRCs are MSI-H, the clinical benefit was very substantial and a similar experience is emerging in clinical practice. The anti-tumor efficacy of a checkpoint inhibitor may well apply to stage III disease where 10-15% of tumors are MSI-H [19].

Targeting PD-L1 is a similarly promising approach to targeting PD-1. In addition to binding to PD-1, PD-L1 is believed to exert negative signals on T cells by interacting with B7, and this interaction is blocked by PD-L1, but not PD-1, antibodies. PD-L1 inhibitors have shown objective anti-tumor responses in patients with a variety of solid tumors including GI malignancies [20-22] and a small number of MSI-H colon cancers (Genentech, unpublished data). As stated, the mechanism underlying the clinical benefit of PD-1/PD-L1 inhibitors in MSI-H tumors is believed to be related to hypermutation [23] with production of mutant proteins and expression of abundant neoantigens that elicit an enhanced immune response [24]. In this regard, neoantigen load is associated with clinical benefit from pembrolizumab in NSCLC and may be predictive in other tumor types [25]. Based primarily on the data for pembrolizumab in metastatic MSI-H tumors, MSI-H is the only biomarker that has been shown to predict the efficacy of checkpoint inhibitor therapy in CRCs. MSI tumors selectively demonstrated highly upregulated expression of multiple immune checkpoints, including five-PD-1, PD-L1, CTLA-4, LAG-3, and IDO [26]. Furthermore, PD-1 and/or PD-L1 may provide prognostic information in patients with nonmetastatic CRCs [27] [28]. Some, but not other, PD-L1-positive cancers have demonstrated higher response rates to anti-PD-1/PD-L1 therapies, suggesting that PD-L1 expression may enrich for anti-tumor responses. However, data indicate that PD-L1-negative tumors can respond favorably to checkpoint inhibitors indicating that PD-L1 is not a universal predictive biomarker. PD-L1 is expressed on immune cells as well as tumor cells in various cancers.

## 1.5 Atezolizumab

Atezolizumab is a humanized IgG1 monoclonal antibody that targets PD-L1 on immune cells and/or tumor cells and prevents interaction with either PD-1 receptor or B7.1 (CD80), both of which function as inhibitory receptors expressed on T cells. Interference of the PD-L1: PD-1 and PD-L1:B7.1 interactions may enhance the magnitude and quality of the tumor-specific T-cell response through increased T-cell priming, expansion, and/or effector function [29]. Atezolizumab was engineered to have minimal binding to Fc receptors and, by eliminating Fc-effector function and antibody-dependent cell-mediated cytotoxicity (ADCC), antibody-mediated clearance of activated effector T cells is eliminated. Overall, the nonclinical pharmacokinetic (PK) behavior observed for atezolizumab is consistent with that expected for a humanized IgG1 monoclonal antibody. Atezolizumab has shown anti-tumor activity in preclinical models and cancer patients, and is being investigated as a single agent in advanced cancer and in adjuvant therapy settings, as well as in combination with chemotherapy, targeted therapy, and cancer immunotherapy. Based upon results from randomized clinical trials, the FDA has granted priority review to atezolizumab, for patients with locally advanced or

metastatic non-small cell lung cancer (NSCLC) who express PD-L1 and have progressed after a platinum-containing regimen. Furthermore, atezolizumab was also granted priority review by the FDA for the treatment of patients with metastatic bladder cancer.

To date, the use of PD-1/PD-L1 inhibitors in combination with chemotherapy has produced promising results in selected tumor types. Several preclinical studies indicate that certain chemotherapeutic agents can have an immunostimulatory effect [30] and in this regard, oxaliplatin can alter tumor immune status to transiently increase inflammation [31] [32]. This so called ‘immune priming’ may extend the inflammatory state to achieve enhanced and more durable responses. Unpublished data from Roche/Genentech indicate that FOLFOX alone or combined with bevacizumab and atezolizumab can increase cytotoxic CD8+ T cells and PD-L1 expression in colorectal metastases which demonstrates immune priming. Data exist for the combination of the PD-L1 inhibitor, atezolizumab (MPDL3280A) with FOLFOX in patients with metastatic CRC. Single agent atezolizumab produced a 7.1% objective response rate (ORR) in 14 MSS CRCs, and responses were also seen for atezolizumab + bevacizumab in MSI tumors although the data remain premature in this subset. A phase I study evaluated the combination of atezolizumab (20 mg/kg q 3 weeks) combined with standard dose FOLFOX plus bevacizumab versus atezolizumab plus bevacizumab in patients with metastatic CRC [33]. In the atezolizumab + bevacizumab + FOLFOX study arm (n=23), there were 12 partial responses with an ORR of 52.2% and a median PFS of 14.1 months vs. an expected mPFS for FOLFOX + bevacizumab of 10-11 months (J Clin Oncol 33, 2015 (suppl. 3; abstr. 704)). All 23 patients had MSS tumors and in the FOLFOX-containing study arm, 70% of patients were previously untreated. A favorable safety profile was observed for both study arms containing atezolizumab and bevacizumab with or without FOLFOX and there was no increase in Grade 3 adverse events (AEs). Atezolizumab is being examined in patients with CRC as part of the biomarker-driven MODUL trial (NCT02291289) [34].

The phase I/II iMATRIX-atezolizumab study (NCT02541604, study GO29664) evaluated the safety, tolerability, PK, immunogenicity, and preliminary efficacy of atezolizumab monotherapy in pediatric and young adult patients with solid tumors [35]. This multicenter, open-label trial enrolled 87 patients with solid tumors with known or expected PD-L1 pathway involvement for which prior treatment was proven to be ineffective or intolerable, and for whom there was no curative standard-of-care treatment. The study included 69 patients aged < 18 years, each of whom received a weight-adjusted dose of atezolizumab (15 mg/kg every 3 weeks [q3w]; maximum 1200 mg). Patients aged 18 years and older received a flat dose (1200 mg q3w). A total of 431 atezolizumab serum concentrations were used for the population-PK (popPK) analysis, which was compared to a prior two-compartment intravenous infusion input adult popPK model. Atezolizumab clearance and volume of distribution estimates were 0.217 L/day and 3.01 L, respectively. Atezolizumab geometric mean trough exposures were ~ 20% lower in pediatric patients versus young adults; this was not clinically meaningful as both groups achieved the target concentration (6 µg/mL). Safety was similar between pediatric and young adult patients with no exposure-safety relationship observed. A comparable rate (13% vs. 11%) of atezolizumab anti-drug antibodies was seen in pediatric and young adult patients. Overall, a similar exposure-safety profile of atezolizumab was demonstrated in pediatric and young adult patients, supporting weight-based dosing in pediatric patients.

### **Safety and Tolerability**

The risks identified in the nonclinical studies conducted with atezolizumab are consistent with the primary pharmacology of PD-L1/PD-1 pathway inhibition. Atezolizumab has been

administered to approximately 3200 patients, with efficacy and safety findings consistent with non-clinical data. No dose limiting toxicities have been observed at any dose level and no maximum tolerated dose (MTD) was established. While inhibition of PD-L1/PD-1 may lead to anti-tumor immune activity and is generally well tolerated, it may also increase the risk of immune-mediated adverse events (IMAEs). Atezolizumab has been well-tolerated as monotherapy with the majority of AEs being Grade 1-2 and manageable (patients continue atezolizumab). The combination of atezolizumab with chemotherapy has not been associated with additive toxicity and is consistent with the known profile for each study treatment. There is long term safety data from randomized trial of atezolizumab versus docetaxel in NSCLC [36] where 11% of patients in atezolizumab groups versus 39% in docetaxel group had treatment related grade 3 to grade 4 adverse events.

## **1.6 Rationale for the Proposed Clinical Trial**

The ability of immunotherapy to unleash a patient's own T cells to kill MSI-H tumor cells is expected to occur in the adjuvant setting, as demonstrated in metastatic disease [37], and may result in reduced recurrence and improved patient survival. The rationale for combination of FOLFOX and atezolizumab is based upon the fact that FOLFOX is standard of care as adjuvant therapy for stage III colon cancer and promising data for combining chemotherapy with atezolizumab, including suggestion of immune priming. Since FOLFOX is standard adjuvant chemotherapy for stage III disease [38], it serves as the control arm for studies aiming to further improve patient outcomes. Atezolizumab will be continued as monotherapy for an additional 6 months following completion of FOLFOX for 6 months (12 cycles). The rationale for this approach is late and sustained responders with the use of pembrolizumab in metastatic MSI-H CRC, the importance of a definitive study, and alignment with ongoing/planned adjuvant studies using atezolizumab in other malignancies. Furthermore, sustained stimulation of the immune system may be key for long-term benefit with immunotherapy. There is a precedent with the anti-CTLA-4 antibody ipilimumab that is approved for the adjuvant therapy of melanoma with treatment duration up to 3 years. We intend for the study outlined in this protocol to be definitive, and regard this study to have the potential to be practice-changing.

## **2.0 OBJECTIVES**

### **2.1 Primary Objective**

To determine whether atezolizumab combined with FOLFOX and its continuation as monotherapy can significantly improve DFS compared to FOLFOX alone in patients with stage III colon cancers and dMMR.

### **2.2 Secondary Objectives**

To determine whether atezolizumab combined with FOLFOX and its continuation as monotherapy can significantly improve overall survival compared to FOLFOX alone in patients with stage III colon cancers and dMMR.

To assess the adverse events (AE) profile and safety of each treatment arm, using the CTCAE and PRO-CTCAE (among patients aged  $\geq 18$  years).

### **2.3 Quality of Life Objective**

The quality of life objective will be to determine the impact of the addition of atezolizumab to FOLFOX on patient-reported neuropathy, health-related QOL, and functional domains of health-related QOL. The quality of life analysis will also assess the efficacy of atezolizumab

adjusting for baseline QOL and fatigue measurements. Patient-reported outcomes will not be assessed in patients aged 12 to <18 years.

## 2.4 Potential Correlative Science Objectives

*Testing of banked specimens will not occur until an amendment to this treatment protocol (or separate correlative science protocol) is reviewed and approved in accordance with National Clinical Trials Network (NCTN) policies.*

- 2.4.1 To determine if the “Immunoscore” can predict the efficacy of atezolizumab for disease-free survival among patients with stage III colon cancer.
- 2.4.2 To assess whether circulating immune cell populations can predict the efficacy of atezolizumab as adjuvant therapy for stage III colon cancer.
- 2.4.3 To explore the associations of genomic alterations identified in cfDNA with DFS in patients treated with FOLFOX with or without atezolizumab.
- 2.4.4 To assess whether soluble markers of systemic inflammation in blood can predict the efficacy of atezolizumab as adjuvant therapy for stage III colon cancer.
- 2.4.5 To assess the relationship between baseline plasma 25(OH) D levels, change in 25(OH)D levels, and DFS and OS in patients with stage III colon cancer receiving FOLFOX +/- atezolizumab.
- 2.4.6 To determine the ability of using fecal microbiota and their metabolic products to predict survival benefit from anti-PD-L1 antibody therapy in dMMR colon cancer patients.
- 2.4.7 To determine if hypermutation or hyper-indel status is associated with response to atezolizumab.
- 2.4.8 To determine if unique mRNA expression signatures are predictive of disease-free survival among patients receiving adjuvant chemotherapy for stage III colon cancer.
- 2.4.9 To determine if the efficacy of atezolizumab differs among dMMR cancers due to germline MMR mutation (MLH1, MSH2, MSH6, PMS2) versus those with MLH1 hypermethylation and CIMP in patients with stage III colon cancer.
- 2.4.10 To identify overall mutational burden and number of putative tumor neoantigens in colon carcinoma specimens.

The following objectives apply to patients aged 12 to <18 years to evaluate the impact of atezolizumab on growth and development patterns in this population:

- 2.4.11 To determine changes in growth patterns compared to baseline (relative to age-specific standards for height and weight).
- 2.4.12 To determine changes in development patterns compared to baseline (relative to onset of menarche [for females] and pubertal changes).

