### Pre-Study Testing Intervals

- To be completed < 28 DAYS before registration: Laboratory studies, history and physical; dMMR testing may be completed at any point prior to registration for the present tumor.
- To be completed ≤ 80 DAYS before registration: Any imaging used to confirm lack of evidence of definitive metastatic disease (pre-surgery scans are acceptable)

	Prior to Registration*	Arm 1: Day 1 of each cycle*	Arm 2: Day 1 of each cycle*	End of treatment follow-up**	Post-treatment follow-up ***
Tests & Observations					
History and Physical, Weight, PS	A	A	A	X	X
Height	X	X(1)	X(1)	X(1)	
Pulse, Blood Pressure	X	X	X	X	
O 2 Saturation	X(2)	X(2)		X(2)	
CTCAE Adverse Event Assessment		X(3)	X(3)	X(3)	X(3)
PRO-CTCAE Adverse Event Assessment	X(4)	X(4)	X(4)	X(4)	
Registration Fatigue/ Uniscale Assessment	X(5)				
Colonoscopy	B				B
Tanner Staging	X(1)	C(1)	C(1)	X(1)	X (1)
Laboratory Studies					
Complete Blood Count, incl. Diff.	X	X	X	X	
Chemistry	X(6)	X(6)	X(6)	X(6)	
TSH	X(7)	X(7)			
Hep B Surface Ag & Hep C ab (Physician Discretion)	X				
Serum or Urine HCG	X(8)				
CEA	X(9)	X(9)	X(9)		X(9)
CD4 Count & Viral Load	X(10)				
dMMR Testing	X				
Staging					
CT of Chest/Abd/Pelvis or MRI of Chest/Abd/Pelvis	D	E	E	E	E
Correlative Studies: For patients who consent to participate					
QOL Assessments	Arm 1: At registration, prior to Cycles 4, 7, and 13, at the end of treatment, and 3 years from registration. Arm 2: At registration, prior to Cycles 4 and 7, at the end of treatment, 12 months from registration, and 3 years from registration. See Sections 6.4, 14.1, and Appendix I .				

Tissue, Blood, and Stool Samples	See Sections 6.2 and 14.2 .
----------------------------------	---

\* Labs and visits completed prior to registration may be used for Day 1 of Cycle 1 (or Day 1 of Cycle 2) tests if obtained  $\leq 14$  days prior to treatment. For subsequent cycles, labs and visits may be obtained  $\leq 2$  business days prior to day of treatment.

\*\* Physical examination, adverse event assessment, labs (CBC and chemistry), and staging scans (if due per footnote D) are required 1 month (+/- 7 days) after the last day of the last treatment cycle.

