\*\*\* Patients will be followed for recurrence every 6 months (+/- 1 month) for the first two years after registration, and then once annually (+/- 1 month) for years 3-5 after registration. Recurrence follow-up will continue per the schedule above for 5 years after registration or until evidence of relapse, whichever comes first. See [Section 12.0](#) for survival follow-up.

- 1 For patients aged 12 to <18 years. Staging should be performed until the patient has reached Tanner Stage V.
- 2 Oxygen saturation should be assessed at rest and after 1 minute walk.
- 3 Solicited AEs are to be collected starting prior to treatment until off-treatment (see [Section 9.1](#)). Routine AEs are to be collected starting after registration until the end of survival follow-up. For patients who complete one cycle of FOLFOX prior to registration, the first routine AE assessment should take place after registration but prior to Day 1 Cycle 2 of FOLFOX; see [Section 9.3](#) for expedited SAE reporting.
- 4 Patients aged  $\geq 18$  years complete PRO-CTCAE by paper booklet ordered through the CTSU website. See [Section 9.1](#) for administration instructions. See [Appendix I](#) for PRO-CTCAE assessments for IRB submission and review only. See [Section 4.3](#) for ordering instructions. PRO-CTCAE booklets should be administered at the following time points:  $\leq 14$  days prior to registration; Day 1 of each Cycle, and at the end of treatment.
- 5 To be completed after registration but  $\leq 21$  days prior to treatment. See [Appendix I](#).
- 6 Albumin, alkaline phosphatase, total bilirubin, bicarbonate (or total CO2), BUN, calcium, chloride, serum creatinine, glucose, potassium, total protein, SGOT (AST), SGPT (ALT), and sodium.
- 7 Perform at baseline and then every 8 weeks (+/- 14 days).
- 8 For women of childbearing potential ([Section 3.2.6](#)). Must be done  $\leq 7$  days prior to registration.
- 9 Perform at baseline, 6 weeks (+/- 7 days) after end of FOLFOX, then every 6 months (+/- 1 month) for 3 years, then every 12 months (+/- 1 month) for an additional 2 years, or until relapse. After the end of FOLFOX treatment, the timing of CEA testing should correspond with timing of radiographic imaging studies, where possible, but more frequent testing is at provider discretion.
- 10 HIV-positive patients should complete a CD4 count and viral load  $\leq 28$  days prior to registration.

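### Height in patients aged 12 to under 18 is not scheduled after the end-of-treatment visit, so the height part of objective 2.4.11 has no concurrent control beyond about 6.5 months and no later follow-up in either arm

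*Combined protocol and SAP*

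**What the plan says.** Section 2.4 of the protocol introduces the two adolescent objectives as being there "to evaluate the impact of atezolizumab on growth and development patterns in this population". Objective 2.4.11 is "To determine changes in growth patterns compared to baseline (relative to age-specific standards for height and weight". Growth is thus defined by height and weight together, as change from each patient's baseline against age norms.

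The Study Calendar in Section 5.0 has five columns: before registration, Day 1 of each cycle in Arm 1, the same in Arm 2, end of treatment, and post-treatment follow-up. Three rows matter:

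- Height: "Height X X(1) X(1) X(1"). Four cells are filled and the post-treatment cell is empty.
- Weight, within the history and physical row: "History and Physical, Weight, PS A A A X X". All five cells are filled.
- Tanner staging: all five cells are filled, including post-treatment follow-up.

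Footnote 1, attached to the height and Tanner rows, reads "For patients aged 12 to <18 years. Staging should be performed until the patient has reached Tanner Stage V". The footnote on the end-of-treatment column says that its assessments "are required 1 month (+/- 7 days) after the last day of the last treatment cycle". Post-treatment visits then run every 6 months to year 2 after registration and yearly to year 5, or until relapse.

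**The concern.** Because height is tied to treatment, its last measurement comes at a different time in each arm. Arm 2 heights stop about half a year before Arm 1 heights, and both stop while the same patients are still being weighed and Tanner-staged at later visits. No reason is given for dropping height alone.

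At stake is whether a change in height can be attributed to atezolizumab. Both arms receive mFOLFOX6, so Arm 2 is what separates a drug effect from the effects of the cancer, surgery and chemotherapy. The protocol makes a growth effect plausible: the endocrine guidance in Section 8.2.2 links atezolizumab to thyroid, adrenal and pituitary disorders and lists growth hormone among the pituitary tests. A lasting effect, or catch-up growth, would show mainly after treatment. A height that is not measured then cannot be recovered later.

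**Working it through.** **Inputs.** Cycle length is 14 days (Section 7.0). Arm 1 has 12 combination plus 13 atezolizumab-alone cycles (Section 7.1), and Arm 2 has 12 cycles (Section 7.2). The end-of-treatment visit comes 1 month, taken here as 30 days, after the last cycle ends, with a window of 7 days either way (Section 5.0). A month is 30.44 days.

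**The plan's own figure.** Arm 1 cycles: 12 + 13 = 25, or 11 + 13 = 24 when one mFOLFOX6 cycle was given before registration. Both match Section 7.1.

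**Last scheduled height = cycles × 14 + 30 days, counted from Cycle 1.**

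- Arm 2: 12 × 14 + 30 = 198 days; 198 / 30.44 = 6.5 months. With the window, 191 to 205 days, or 6.3 to 6.7 months.
- Arm 1: 25 × 14 + 30 = 380 days; 380 / 30.44 = 12.5 months. With the window, 373 to 387 days, or 12.3 to 12.7 months.
- If one cycle preceded registration, counting from the first on-study cycle: Arm 2, 11 × 14 + 30 = 184 days (6.0 months); Arm 1, 24 × 14 + 30 = 366 days (12.0 months). Counting from registration adds up to 14 days. Over all variants the ranges are 5.8 to 7.2 months in Arm 2 and 11.8 to 13.2 months in Arm 1.

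**What is uncontrolled.** The gap between the arms' last heights is 380 − 198 = 182 days, the same length as 13 × 14 = 182 days of atezolizumab alone. That phase runs from day 168 to day 350. The last Arm 2 height, at day 198, falls 30 days into it, so 350 − 198 = 152 of its 182 days have no concurrent control height.

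**What continues without height.** Visits run to month 60. That is 60 − 6.5 = 53.5 months after the Arm 2 end-of-treatment visit and 60 − 12.5 = 47.5 months after the Arm 1 visit, with weight throughout and Tanner staging until Stage V.

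**How far off drug the last Arm 1 height is.** The last infusion is on Day 1 of the last cycle, so the visit falls 14 + 30 = 44 days later. With the 27-day half-life in Section 10.5, 44 / 27 = 1.6 half-lives. On simple exponential decline, 0.5^1.63 = 0.32, so about a third of the drug remains.

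**Scale, on an outside assumption.** The documents give no height velocity. At an assumed 5 cm/year (range 2 to 8), growth by day 198 is 5 × 198/365 = 2.7 cm (1.1 to 4.3), and by day 380 it is 5 × 380/365 = 5.2 cm. For a patient at or near adult height, both figures approach zero.

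**The case against.** A reader might infer that the growth objective has no comparison after 6.5 months and no post-treatment data at all. The documents do not support that, for three reasons:

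- Objective 2.4.11 also names weight, which is scheduled in both arms to year 5 or relapse. Weight-for-age is itself an age standard, so weight without height is a weaker measure of linear growth but not an unusable one.
- The objective's stated comparators are baseline and age norms, not the other arm. On that wording Arm 1 height can be assessed to about 12.5 months, across the whole atezolizumab course. The stated purpose makes a concurrent control desirable; it does not make the objective unanswerable without one.
- The end-of-treatment height is taken about a month after the last cycle in each arm, so one off-treatment height exists, although in Arm 1 it is not far off drug.

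Numbers also limit what any schedule can show. These are potential correlative objectives with no sample size or analysis in Section 13, and patients under 18 are outside the 700 (Section 13.2). A between-arm comparison would be descriptive however long height were followed. That stands, but it does not justify the gap. With few patients, each full growth curve is the usable evidence. The deferral in Section 2.4 concerns testing of banked specimens, which can wait; a height cannot.

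Three further points carry little weight. The warning in Section 10.5 about delayed side effects is general nursing guidance and does not mention growth. No calendar row names menarche, but the case report forms are not among these documents, so whether it is captured cannot be judged. The empty cell is unlikely to be a PDF artefact, since the row fits the five columns in the same way as the pulse and blood pressure row.

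**Conclusion.** The point holds for height only. Height is the one growth or development measure in the calendar that stops at the end-of-treatment visit: about 6.5 months in Arm 2 and 12.5 months in Arm 1. Concurrent control for height ends at about day 198, roughly one month into the atezolizumab-alone phase, and no height follows in either arm over the remaining 53.5 and 47.5 months of scheduled visits. Weight in both arms, Tanner stage in both arms, and Arm 1 height against norms to 12.5 months remain available.

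The dates assume that all planned cycles are given without delay. A patient who stops early has the last height earlier still, and delays move it later. The growth figures in centimetres rest on an assumed velocity and only indicate scale.

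This is a modest design improvement. It touches no primary or secondary endpoint, no safety rule and no powered analysis.

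**What to change.** In Section 5.0, mark height with footnote 1 in the post-treatment follow-up column, so that it is measured in both arms at the visits that already include weight and Tanner staging. State that change in height-for-age will be summarised descriptively by arm at common times from registration, for example 6, 12, 18 and 24 months. The Day 1 and end-of-treatment heights already serve the early times; the added cell supplies Arm 2 at 12 months and both arms after that.

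The cost is one extra measurement and one form field per follow-up visit in a small number of adolescents, with no additional visits. Any contrast between the arms would stay descriptive and should be labelled so.
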